#### 9.5.3 Pharmacogenetic Assessments

An optional blood sample will be collected from all subjects providing consent and may be analyzed to explore the impact of polymorphisms in genes encoding drug metabolizing enzymes and/or transporters (e.g., cytochrome P450 CYP2C9, CYP2D6, solute carrier organic anion

Fipaxalparant (HZN-825)
Protocol: HZNP-HZN-825-303
Version 5.0, Amendment 4

transporter family member [SLCO] 1B1 and SLCO1B3) on fipaxalparant (HZN-825) PK. These samples will be stored no longer than 5 years.

Instructions for collection, processing, handling, storing and shipping of samples will be detailed in a laboratory manual that will be provided to each site prior to site initiation.

### 9.5.4 Pharmacodynamic Assessments

Blood samples will be taken during the trial to evaluate the pharmacodynamic effect of fipaxalparant (HZN-825). Serum samples will be taken at the following visits: Day 1 (predose), Week 16 (pre-dose), Week 28 (pre-dose), Week 52 (pre-dose), Week 80 (pre-dose) and Week 104 (pre-dose). Samples will be stored frozen for potential analysis of biomarkers of the LPAR1 pathway or IPF disease. All samples will be destroyed after potential biomarkers have been tested or 5 years after the trial is complete, whichever comes first.

A blood sample will be taken at Day 1 (pre-dose), Week 28 (pre-dose), Week 52 (pre-dose), Week 80 (pre-dose) and Week 104 (pre-dose) for gene expression profiling of peripheral blood mononuclear cells as it relates to disease biology. Instructions for collection, processing, handling, storing and shipping of samples will be detailed in a laboratory manual that will be provided to each site prior to site initiation.

# 9.5.5 Safety Variables

Safety will be assessed via AEs, concomitant medication use, physical examinations, vital signs, orthostatic hypotension assessment, laboratory evaluations, 12-lead ECG, and echocardiogram.

#### 9.5.5.1 Adverse Events

#### **9.5.5.1.1 Definitions**

#### 9.5.5.1.1.1 Adverse Event Definition

According to ICH, an AE is any untoward medical occurrence in a patient or clinical investigation subject administered a pharmaceutical product and which does not necessarily have a causal relationship with this treatment. An AE can therefore be any unfavorable and unintended sign (including an abnormal laboratory finding), symptom or disease temporally associated with the use of a medicinal (investigational) product, whether or not considered related to the medicinal (investigational) product.

A suspected adverse reaction means any AE for which there is a reasonable possibility that the drug caused the AE. Reasonable possibility means there is evidence to suggest a causal relationship between the drug and the AE.

Exacerbation of a chronic or intermittent pre-existing condition that worsens in intensity or increases in frequency during a trial is to be reported as an AE.

Unchanged, chronic conditions are **NOT** considered AEs and should not be recorded on the AE pages of the eCRF unless there is a clear exacerbation of a chronic condition.

Disease progression can be considered as a worsening of a subject's condition attributable to the disease for which the trial drug is being studied (i.e., IPF). It may be an increase in the severity of the disease under study and/or increases in the symptoms of the disease. Events that are unequivocally due to disease progression should only be reported as AEs if they fulfill any of the SAE criteria or are the reason for discontinuation of trial drug.

# 9.5.5.1.1.2 Serious Adverse Event Definition

A TEAE, baseline event or suspected adverse reaction is considered serious if, in the view of either the Investigator or Sponsor, it results in any of the following:

- Death. This includes any death that occurs during the conduct of a clinical trial, including deaths that appear to be completely unrelated to the trial drug (e.g., car accidents).
- Life-threatening adverse experience. An AE or suspected adverse reaction is considered life-threatening if, in the view of either the Investigator or the Sponsor, its occurrence places the subject at immediate risk of death. It does not include an AE or suspected adverse reaction that, had it occurred in a more severe form, might have caused death.
- Persistent or significant disability or incapacity.
- Inpatient hospitalization or prolongation of an existing hospitalization.
- Congenital anomaly or birth defect.
- Other medically important event that, according to appropriate medical judgment, may require medical or surgical intervention to prevent one of the outcomes listed above.

Surgical procedures or other therapeutic interventions themselves are not AEs, but the condition for which the surgery/intervention is required is an AE and should be documented accordingly.

Elective surgeries that require hospitalization and treatment received at an emergency room or similar facility will not be considered as SAEs unless one of the definitions of an SAE listed above is met.

In addition, hospitalizations for planned procedures are not considered an AE, unless they are prolonged hospitalizations and emergency room visits <24 hours in duration are not considered hospitalizations.

#### 9.5.5.1.1.3 Non-serious Adverse Event Definition

A non-serious AE includes any AE that is not described in the previous SAE category.

# 9.5.5.1.1.4 Adverse Events of Special Interest

An AESI is an AE (serious or non-serious) of scientific and medical concern specific to the Sponsor's product or program, for which ongoing monitoring and rapid communication by the Investigator to the Sponsor may be appropriate. Such events may require further investigation in

order to characterize and understand them. AESIs may be added or removed during a trial by protocol amendment.

The following AESI is identified for this trial:

• Orthostatic hypotension: The Sponsor will consider an event of orthostatic hypotension if the following definition is met: a reduction of systolic BP by ≥20 mmHg or reduction of diastolic BP by ≥10 mmHg and associated with symptoms such as lightheadedness, blurred vision, weakness, fatigue, cognitive impairment, nausea, palpitations, tremulousness, headache, presyncope or syncope.

The symptoms i.e., lightheadedness, blurred vision, weakness, fatigue, cognitive impairment, nausea, palpitations, tremulousness, headache, presyncope, or syncope are reported by the patient throughout the orthostatic hypotension assessment, without the BP reductions (reduction of systolic BP ≥ 20 mmHg or diastolic BP ≥10 mmHg), then these symptoms will be recorded as AE.

Please note that the above-mentioned reported symptoms during orthostatic hypotension assessment should only be reported as adverse events separately if they meet any of the below criteria:

- The symptoms are severe and/or require medical interventions
- The symptoms were triggered by the orthostatic hypotension assessment maneuver and persisted for a significantly longer duration beyond the orthostatic hypotension assessment period
- The symptoms are assessed not due to the maneuver of orthostatic hypotension assessment

If these symptoms are reported in combination with the BP reductions, i.e., reduction of systolic BP  $\geq$ 20 mmHg or diastolic BP  $\geq$ 10 mmHg, these symptoms will be considered part of the orthostatic hypotension event and will not be reported separately.

Orthostatic hypotension assessment procedure will be performed during the Core Phase (as outlined in Section 2.1 on Day 1 and at Weeks 4, 28, and 52/premature discontinuation) and the Extension Phase (as outlined in Section 2.2 on Day 1 [Week 52 of Core Phase] and at Weeks 56, 80 and 104/premature discontinuation), as is detailed in the Orthostatic Hypotension Assessment Manual in Section 17.9.

If symptoms are reported by the subject throughout the assessment, without the BP reductions noted above, then the symptoms will be recorded separately as AEs and orthostatic hypotension will not be recorded.

Signs and symptoms associated with orthostatic hypotension reported outside of the assessment will be captured as part of spontaneously reported AEs at each visit.

Protocol: HZNP-HZN-825-303 Version 5.0, Amendment 4

Fipaxalparant (HZN-825)

Depending on the timing, nature and severity of these spontaneous AEs, additional investigations will be conducted at the next scheduled visit or at an unscheduled visit, as clinically indicated per the Investigator's judgment. Whenever possible, the following data should be collected: concomitant medications, and BP and heart rate measurements in supine and standing positions. Depending on the severity, plasma glucose level and ECG should be obtained per Investigator's clinical judgment.

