### Orthostatic Hypotension Assessment Manual

## Safety Vital Signs (Supine and Orthostatic) Per Protocol

Information about the orthostatic hypotension assessment and its intended use:

- This assessment is purposed to inform whether treatment with HZN-825 is associated with orthostatic hypotension. This assessment is part of the overall safety evaluation of the current protocol.
- 2. This data is being collected as part of the overall safety analysis for the current trial.

The supine and orthostatic vital signs, as outlined in the protocol along with safety assessments, will be performed using either a standard manual or automated blood pressure cuff. A single measurement will be captured at each of the timepoints as indicated in the protocol and reviewed accordingly. For this assessment, heart rate and systolic and diastolic blood pressure will be measured after 5 minutes in supine resting position followed by measurement after 1 minute and 3 minutes in the standing position.

Positive orthostatic hypotension test is defined as the combination of a reduction of systolic blood pressure by  $\geq 20$  mmHg or reduction of diastolic blood pressure by  $\geq 10$  mmHg, and the presence of one or more of the following associated clinical symptoms:

 lightheadedness, blurred vision, weakness, fatigue, cognitive impairment, nausea, palpitations, tremulousness, headache, presyncope or syncope

If positive for orthostatic hypotension, as defined above (inclusive of clinical symptoms), the subject should be assisted to lie back down in the supine position and monitored for clinical resolution of symptoms.

Prior to beginning the procedure, patients should be instructed to report any symptoms experienced throughout the assessment without probing for specific types of adverse events. If any symptoms occur during the assessment in combination with the blood pressure reductions noted above, they are considered as part of the orthostatic hypotension event and will not be recorded separately as individual adverse events.

If above symptoms are reported by the patient throughout the assessment, without the blood pressure reductions noted above, then the symptoms will only be recorded separately as adverse events if they meet any of the criteria below, and orthostatic hypotension will not be recorded.

- The symptoms are severe and/or require medical interventions

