## Lying Supine and Standing Pulse and Blood Pressure Test (See diagram 1)

#### A. Lying Supine

- Subject should lay supine for approximately 5 minutes (+/- 1 minute), while practicing quiet breathing.
- At the end of approximately 5 minutes (+/- 1 minute), the heart rate and blood pressure will be measured.
- Both assessments of heart rate and blood pressure (including systolic and diastolic) will be collected.
- B. Subject stands upright One Minute Assessment upon standing
  - 1. The subject should change positions from supine to standing.
  - Blood pressure and heart rate will be measured after the subject has been standing for 1
    minute.
  - 3. Both assessments of heart rate and blood pressure will be collected.
- C. Subject remains standing upright Three-Minute Assessment after the subject has stood up
  - Blood pressure and heart rate will be measured after the subject has been standing for 3
    minutes.
  - 2. Both assessments of heart rate and blood pressure will be collected.

The symptoms i.e. lightheadedness, blurred vision, weakness, fatigue, cognitive impairment, nausea, palpitations, tremulousness, headache, presyncope or syncope are reported by the patient throughout the OH assessment, without the blood pressure reductions (reduction in systolic BP  $\geq$  20 mmHg or diastolic BP  $\geq$ 10mmHg), then these symptoms will be recorded as adverse events. Please note that the above-mentioned reported symptoms during OH assessment should only be reported as adverse events separately if they meet any of the below criteria:

- The symptoms are severe and/or require medical interventions
- The symptoms were triggered by the OH assessment maneuver and persist for a significantly longer duration beyond the OH assessment period
- The symptoms are assessed not due to the maneuver of OH assessment

If these symptoms are reported in combination with the blood pressure reductions i.e. reduction in systolic BP  $\geq$  20 mmHg or diastolic BP  $\geq$  10 mmHg, these symptoms will be considered part of the orthostatic hypotension event and will not be reported separately.

Version 3.0, Dated 14 June 2023

[figure not shown]
Page 2 of 3

Fipaxalparant (HZN-825)
Protocol: HZNP-HZN-825-303
Version 5.0, Amendment 4

HZNP-HZN-825-301

Orthostatic Hypotension Assessment Manual

Diagram 1 - Lying Supine and Standing Pulse and Blood Pressure Steps

Record all measurements on CRF

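### A stand-alone sentence in Protocol 9.5.5.1.1.4 makes every symptom without a BP drop during the orthostatic assessment an AE, while the rest of the section and the manual make it an AE only under three criteria

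*Protocol*

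**What the plan says.** Protocol 9.5.5.1.1.4 defines the trial's one AESI, orthostatic hypotension, as a systolic or diastolic reduction of stated size together with symptoms. It then addresses symptoms that occur during the assessment without that reduction, and does so in three places.

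- An earlier paragraph says "then these symptoms will be recorded as AE".
- A note directly after it says the symptoms "should only be reported as adverse events separately if they meet any of the below criteria". The criteria are that the symptoms are severe or need medical intervention, that they persist significantly beyond the assessment, or that they are not due to the maneuver.
- A later paragraph, after the one giving the assessment schedule, returns to the case and says "then the symptoms will be recorded separately as AEs and orthostatic hypotension will not be recorded". It has no criteria and no cross-reference to them.

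The Orthostatic Hypotension Assessment Manual (Version 3.0, reproduced in Protocol 17.9) covers the same case twice. Its introductory part builds the condition into the sentence: "then the symptoms will only be recorded separately as adverse events if they meet any of the criteria below". Its step-by-step part first says "then these symptoms will be recorded as adverse events" and follows at once with the same limiting note and the same three criteria.

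SAP 7.1.6 has spontaneously reported orthostatic-type signs and symptoms captured as AEs, identified by a dataset flag and/or a standard MedDRA query (SMQ). It lists the results of the orthostatic assessment. It does not say how symptoms arising during the assessment without a BP drop are to be treated.

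**The concern.** A site that follows the later paragraph of 9.5.5.1.1.4 records a brief lightheaded spell on standing, without a BP drop, as an AE. A site that follows the limiting note or the manual does not. Both are following current Version 5.0 text.

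The affected terms lie close to the trial's only AESI: lightheadedness, nausea, headache, fatigue, presyncope and the others on the protocol's list. If practice differs among about 85 sites, the incidence of these terms partly reflects which paragraph a site applied.

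The tables are sensitive to small counts. SAP 7.1.5.1 summarizes TEAEs occurring in more than 5% of subjects in any treatment group. With 45 subjects per group, two subjects give 2/45 = 4.4% and three give 3/45 = 6.7%, so a third recorded case brings a term into that summary.

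**Working it through.** The plan states no figure to reproduce, so the check is a comparison of the current statements of the rule, followed by a count of the assessments exposed.

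**Step 1: the statements side by side, for symptoms without the BP reduction.**

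| Place | Rule as written | Qualified nearby? |
|---|---|---|
| Protocol 9.5.5.1.1.4, earlier paragraph | Record as AE | Yes, by the note directly after it |
| Protocol 9.5.5.1.1.4, note | AE only if a criterion is met | Is itself the condition |
| Protocol 9.5.5.1.1.4, later paragraph | Record as AE | No |
| Manual (17.9), introductory part | AE only if a criterion is met | Condition inside the sentence |
| Manual (17.9), step-by-step part | Record as AE | Yes, by the note directly after it |

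Only the later protocol paragraph cannot be read as conditional. Its sentence is nearly the manual's introductory sentence without the condition; both end by saying that orthostatic hypotension is not recorded.

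**Step 2: where the two rules give different answers.**

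- BP drop with symptoms: part of the orthostatic hypotension event, not recorded separately. Same result.
- No BP drop, any criterion met: AE under both. Same result.
- No BP drop, no criterion met (non-severe, untreated, not persisting, due to the maneuver): AE under the unconditional sentence, no AE under the criteria. Different result.
- Symptoms outside the assessment: captured as spontaneous AEs whichever rule is used. Same result.

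**Step 3: effect on the AESI count.** The definition needs a BP drop and symptoms. Symptoms alone never meet it, so the AESI count does not change.

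**Step 4: assessments exposed.**

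- Core Phase schedule: Day 1 and Weeks 4, 28 and 52 (Protocol 9.5.5.1.1.4).
- Day 1 assessments come before the first dose (Protocol 2.1, footnote 2), and events before dosing count as medical history (Protocol 9.5.5.1.2). That leaves three assessments at which a TEAE could arise.
- Planned size: 135 subjects, 45 per group (Protocol 9.6.3).
- Core maximum: 135 x 3 = 405 assessments, or 45 x 3 = 135 per group, assuming no dropout.
- Extension: Day 1 is the Core Week 52 visit, so it adds three per subject (Weeks 56, 80 and 104).

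**Step 5: number of AEs affected.** This would be the exposed assessments multiplied by the rate of symptoms in the disputed category. The documents give no such rate, so it cannot be computed.

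**The case against.** The strongest defense is that the intended rule is clear and only one leftover sentence departs from it. In the earlier protocol paragraph and in the manual's steps, the unconditional statement and the note read naturally as a rule and its limit. The summary of changes gives the conditional rule as the purpose of manual Version 3.0 and says its revisions went to all sites by memo on 12 June 2023. Section 9.5.5.1.1.4 itself sends sites to that manual. Core sites are blinded, safety summaries are descriptive, and the assessment results are listed.

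Most of this stands. It narrows the problem and makes actual divergence between sites a possibility, not a demonstrated fact. It does not remove the later paragraph, which is operative protocol text and carries no condition. A site must reconcile it with the manual unaided. The SAP does not help: it states that it is based on protocol Version 4.0 and has no rule for separating symptoms recorded under one reading from those recorded under the other.

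A reader might infer more than the documents support:

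- That the AESI incidence is in doubt. It is not (Step 3).
- That AE rates for these terms are uninterpretable, or that a dose difference is diluted. Neither can be shown without a symptom rate.
- That all four Core assessments count, giving 135 x 4 = 540. Day 1 precedes dosing and does not yield TEAEs.

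**Conclusion.** The inconsistency is real and lies wholly within current protocol text. It rests on one stand-alone sentence in 9.5.5.1.1.4, against the note in the same section and both parts of the manual. It affects a single category: non-severe, untreated, transient, maneuver-induced symptoms without a BP drop.

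The exposure is at most 405 post-first-dose Core assessments plus three per extension subject. These are ceilings that assume 135 treated subjects and no missed visits. The number of AEs affected is unknown.

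The consequence is that symptom TEAE counts, and any SMQ-based search that draws on them, may not be comparable across sites. Because Core sites are blinded, inconsistent use of the rules would be expected mainly to add variation between sites; bias between arms is not shown. The point should be corrected because an AE-recording rule next to the only AESI should have one reading and the correction is cheap.

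**What to change.** Reconcile Protocol 9.5.5.1.1.4 and the manual in 17.9 so that both carry one recording rule. In practice, delete or qualify the later stand-alone sentence, and merge each unconditional sentence with the note that follows it, in the protocol section and in the manual's steps, into a single statement.

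In SAP 7.1.6, state how symptoms already recorded under the other reading are handled in the TEAE and SMQ summaries.

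A field marking symptoms that arose during the assessment would let both counts be reported. It is optional, because the case report form is not among the documents and may already capture this.

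The cost is wording in the protocol and manual, a short SAP addition and a clarification to sites. No assessment, visit or sample size changes.

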#### 9.5.5.1.2 Documentation of Adverse Events

Any AEs that occur after signing the ICF and prior to dosing on Day 1 will be considered medical history. The TEAE reporting period begins with administration of the first dose of trial drug on Day 1 and continues until 4 weeks after the last dose of trial drug or premature discontinuation. All medical history, TEAEs and AEs must be recorded in the source documents and on the subject's eCRF. All AEs and SAEs with onset after signing of informed consent through 4 weeks after the last dose of trial drug will be recorded. If a subject discontinues due to an SAE, that subject will be followed as per Section 9.5.5.1.5.

If the Investigator observes an SAE after trial completion that he/she believes was possibly caused by trial drug, the Investigator will report this SAE using the procedures described in Section 9.5.5.1.5. The Investigator is responsible for collecting and documenting the outcome of AEs/SAEs.

If specifically requested, the investigator may need to provide additional follow-up information, such as discharge summaries, medical records, or extracts from the medical records. In this case, all subject identifiers, except for the subject number, will be blinded on the copies of the medical records before submission to the Sponsor.

Detailed information regarding all SAEs must also be recorded on the SAE Reporting Form. Whenever clinically appropriate, the Investigator should group together into a single term the signs and symptoms that constitute a single diagnosis. For example, cough, rhinitis and sneezing might be grouped together as "upper respiratory infection" if the Investigator is confident of the diagnosis.

